### **7.3 RATIONALE FOR THE STUDY**

The collection of data under conditions of routine clinical practice is important for studying large patient numbers that include a broad spectrum of co-morbidities and co-medication use with the use of a new drug. Observational studies can provide supplementary data, including safety data with available doses of NOACs (e.g., 75 mg, 110 mg and 150 mg dabigatran etexilate) and health care resource utilization. This can complement previously collected data from randomized clinical trials, which generally have stricter entry criteria and structured monitoring schemes. This can lead to the exclusion of significant patient segments. But even patients theoretically eligible might often not be included in clinical trials, especially older, frail, and presumably non adherent/persistent patients. These facts make it desirable to generate high-quality non-trial data to complement the evidence obtained from clinical trials.

With the recent approval of NOACs for the treatment and prevention of recurrent VTE, the use of older, traditional treatments, such as VKA, may change, and it is therefore important to understand how patients with different characteristics are treated under conditions of routine clinical practice. In addition, there may be geographical or regional differences in treatment patterns based on a number of factors, including patient co-morbidities and co-medication use or cost and access to newer therapies.

Dabigatran etexilate safety and efficacy with the 150 mg b.i.d. dose has been demonstrated in large randomized clinical trials for several indications (e.g., VTE, stroke prevention in AF). However, the safety and effectiveness of 110 mg b.i.d. dabigatran etexilate compared with VKA for treatment of VTE has not been investigated in randomized clinical trials. Health

authorities, however, have requested the lower dose (110 mg b.i.d) for use in the treatment of VTE in special populations (e.g., elderly or patients concomitantly taking verapamil). This observational study provides an opportunity to collect clinical data in a broader patient population including all available dosages of dabigatran etexilate.

## **8. RESEARCH QUESTION AND OBJECTIVES**

There are two primary objectives in this study:

**Objective 1:** To characterize the DVT / PE patient population including the initial acute event phase. All patients with a DVT and/or PE will be enrolled for cross-sectional characterization of the VTE patient population and descriptions of current treatment patterns, and stratified by geographical location.

**Objective 2:** To analyze the safety and effectiveness of dabigatran etexilate regimens in the treatment of DVT and PE over 1 year of follow-up in comparison to a VKA regimen.

Additional further exploratory objectives are:

- To evaluate geographical variations in health care resource utilization and patient satisfaction with their treatment in routine clinical practice.
- To conduct stratified analysis for the safety and effectiveness of dabigatran etexilate according to dose.

The following research questions will be investigated:

- With the approval of dabigatran etexilate and other NOACs, what treatments are being administered for acute VTE in routine clinical practice in the different regions of the world?
- When presenting with an acute VTE event, what factors influence the choice of treatment for the event?
- What is the safety and effectiveness of dabigatran etexilate versus VKA under conditions of routine clinical practice?
- What health care resources are utilized in patients who are treated with dabigatran etexilate or VKA for an acute VTE under conditions of routine clinical practice?
- For patients who are treated with either dabigatran etexilate or VKA, what is patients' satisfaction with their treatment under conditions of routine clinical practice?

## 9. RESEARCH METHODS

### 9.1 STUDY DESIGN

RE-COVERY is a large, multi-national, multi-center observational study based on new data collection. The study will enroll and characterize all patients diagnosed with an acute DVT and/or PE. Patients treated with dabigatran etexilate or VKA will be followed up for the occurrence of outcome events for up to one year. The design is outlined in Figure 9.1:1.

To investigate [Objective 1](#), a cross sectional design is selected to characterize the DVT/PE patient population at the time of an acute VTE event. The goal is to consecutively enroll approximately 6000 patients, who suffer from a DVT/PE independent of initial treatment choice and to allow for characterization of treatment patterns under conditions of routine clinical practice. Sites should utilize consecutive unselected enrollment (i.e., each patient who is seen with a VTE should be enrolled regardless of what treatment was provided) to avoid bias associated with preferential selection by physicians / site staff for the first objective (characterization of patient population). Patients should be enrolled ideally within 14 days of their acute VTE however sites will have up to 6 months to enroll the patient.

For [Objective 2](#), that will compare patients who are being treated with dabigatran etexilate or VKA, a cohort design was selected to allow for comparisons between the two groups of patients regarding major and clinically relevant non-major bleeding events (primary safety outcome measure), and symptomatic recurrent DVT and PE events, including VTE-related mortality (primary effectiveness outcome measure). For the second objective, a balanced enrollment approach should be used so that the number of VKA patients does not vastly outnumber the dabigatran etexilate patients and both patient groups are collected at similar time points (i.e., for each dabigatran etexilate patient enrolled, the next VKA patient with the same index event (DVT/PE) should be recruited ideally at the same study site). Since the severity of the disease, treatment patterns and patient characteristics may differ considerably between patients with a DVT versus a PE, the treatment arms should have roughly equal numbers of patients with DVT and PE. To ensure global representation, regional recruitment caps will be employed to minimize under-or over-representation from a particular region. Patients should be enrolled ideally within 14 days but not more than 30 days of their acute VTE.

[figure not shown]

Figure 9.1:1 Study design

## 9.2 SETTING

It is planned that approximately 6000 patients will be enrolled for [Objective 1](#) and up to 5000 patients will be enrolled for [Objective 2](#) from approximately 300 sites around the world.

[figure not shown]

Figure 9.2:1 Enrollment of patients into the study

Participating countries require the approval of dabigatran etexilate for the VTE indication prior to study initiation within that country. Selected sites should include those physicians (e.g., specialists and general practitioners) and facilities (e.g., general practice offices, specialist offices, hospitals, outpatient-care centers and anticoagulation clinics) that reflect the clinical practice within that country. A robust site feasibility process will be undertaken to ensure that the participating sites represent the standard of care within that country. A pre-screening log will record minimal information about all potential patients (e.g., all patients who present with a VTE, age and gender will be collected if permissible by local law and if patient provided consent to participate in the study). This log will be maintained in the Investigator site file (ISF).

### **9.2.1 Inclusion criteria**

1. Written informed consent provided by the patient or the patient's legal representative in accordance with local regulations
2. Diagnosis of an acute DVT irrespective of location and/or PE (For objective 1, assessment of patient for study participation should be done ideally within 14 days but not more than 6 months after diagnosis of the acute VTE. For Objective 2, patient assessment should occur ideally within 14 days but not more than 30 days from diagnosis)
3. Age  $\geq$  18 years
4. For [Objective 2](#), the planned anticoagulation therapy should be for at least 3 months
5. For Objective 2, dabigatran etexilate and VKA patients should be available for follow-up data collection (clinic or via phone) at the specified timeframes

### **9.2.2 Exclusion criteria**

1. On active or prophylactic anticoagulation therapy for conditions other than VTE. Ongoing anticoagulation treatment due to history of previous VTE is not considered an exclusion criterion. Anticoagulation therapy given for planned surgery is not considered an exclusion criterion.
2. Current participation in a clinical trial for VTE indication or current use of an unapproved (i.e., investigational) drug

The exclusion criteria were chosen for safety reasons and the number of patients thus excluded should be minimal.

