#### Follow-up

Only patients who are treated with dabigatran etexilate or VKA are eligible to participate in the second objective that will include follow-up for up to 12 months after the index event. Balanced enrollment should be followed with regards to the treatment (i.e., dabigatran etexilate or VKA) and the type of index event (e.g., DVT or PE or DVT and PE). The decision to enroll a dabigatran etexilate or VKA patient for follow-up should be made as soon as the dabigatran etexilate or VKA has been prescribed and the patient has signed the study informed consent form (in accordance with local regulations). Patients should not be excluded from participation due to early outcome events (e.g., bleeding events). Data from all visits conducted under usual practice should be recorded in the electronic data capture (EDC) system at each data collection time-point even if the patient stops or changes treatment for the VTE event. Follow-up should be conducted by in-person clinic visits ideally. However, if no follow-up clinic visit occurs as part of clinical practice within one month of the planned data collection time-point (refer to Table [9.3.1:2](#)), then follow-up contact with patient will be done by telephone, and email, if available.

If a patient discontinues the study for any reason, a follow-up assessment should be performed at the time of study discontinuation, if possible.

If the treatment for a patient changes during the study the following guidance should be followed:

- An objective 1 patient whose anticoagulation treatment is switched to DE or VKA can be enrolled into objective 2 as long as inclusion criteria 2 and 4 are met
- An objective 2 patient whose anticoagulant treatment is switched will be followed-up per protocol, including ePROs
- An objective 2 patient who stops taking anticoagulation treatment will be followed-up per protocol but will discontinue ePROs.

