6. GENERAL ANALYSIS DEFINITIONS

6.1 EXPOSURE

Patients will be analyzed in treatment groups (DE or VKA) according to the treatment that has been prescribed at the baseline visit and at hospital discharge or 14 days after the baseline visit and recorded in the Patient Status eCRF (obtained at enrolment). The start of the follow up will be defined as the initiation of each of these two treatments.

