6.7 BASELINE, TIME WINDOWS AND CALCULATED VISITS

The baseline analysis for Objective 2 is cross-sectional in nature. Patients will be assigned to the two treatment groups as described in Section 6.1. For the descriptive analysis, in addition to the data collected at the baseline visit, additional data at hospital discharge or 14 days after the baseline visit (whichever is later) will be collected and summarized descriptively. For the logistic regression analysis to produce estimated propensity scores, data up to the start of dabigatran or VKA treatment will be considered as baseline and will be used as model covariates.

Data from the longitudinal follow-up for collected laboratory data, healthcare resource utilization, and PACT-Q2 will be summarized descriptively at the time points given in [Table 5.3: 2](#). In case time windows will be needed in order to assign observations to visits, observations from 45 days to 134 days after diagnosis will be assigned to month 3, from 135 days to 269 days after diagnosis will be assigned to month 6 and more than 269 days will be assigned to year 1. In case more than one observation is assigned to a certain visit the observation closest to the calculated visit will be assigned. In case two or more observations are on the same day the last will be assigned. Month 3 corresponds to 91 days, month 6 to 182 days, and year 1 to 365 days.

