7.6 MAIN ANALYSIS

Analyses for the main outcome events are mainly defined for patients in the restricted patient set and, in some occasions for patients in the eligible patient set who took at least once the treatment. In general, recurrent events will be disregarded for the analyses of the outcomes.

Main outcome events – Incidence rates

For the treatment groups incidence rates with 95% CIs, cumulative risks, and KM curves will be calculated on the eligible patient set. Only patients from the eligible patient set that took the prescribed treatment at least once are considered. Patients who complete the planned anticoagulation treatment prior to one year or discontinue initial anticoagulation treatment permanently will be censored at date of last drug intake + 6 days for both DE and VKA or at first intake of another relevant anticoagulation treatment, whichever occurs first. A patient is considered to have permanently stopped initial anticoagulation treatment if other relevant anticoagulation treatment is initiated or if treatment has been interrupted for more than 30 days.

The main analysis of overall incidence rates with 95% confidence intervals, cumulative risks and KM curves will be repeated for the subgroups defined in Section 6.4. A graphical (forest-plot-like) display will additionally be prepared to summarize the subgroup results per outcome on the eligible patient set. Additional subgroup analyses might be conducted as needed.

For all important main and secondary outcomes for patients initiating VKA at baseline, and patients initiating DE at baseline, incidence rates, cumulative risks with 95%-confidence intervals will be calculated by treatment, and for a graphical comparison Kaplan Meier curves

will be plotted. These statistics will be calculated on the restricted patient set, and patients who never took the prescribed treatment will not be included. For the restricted patient set, as a sensitivity analysis, the calculation of incidence rates and cumulative risks will be performed without censoring at permanent discontinuation (intention to treat (ITT) approach). KM curves will be plotted.

Secondary and further outcome events

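### Objective 2 admits patients already anticoagulated at the index VTE and patients switched early, but the visible DE versus VKA analysis has no term for either and no defined start date for ongoing users

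*Protocol*

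**What the plan says.** **Who may enter.** Protocol 9.2.2, exclusion 1, bars anticoagulation for conditions other than VTE but adds that "Ongoing anticoagulation treatment due to history of previous VTE is not considered an exclusion criterion". No separate rule is given for Objective 2. Protocol 9.2.4 (Follow-up) adds that "An objective 1 patient whose anticoagulation treatment is switched to DE or VKA can be enrolled into objective 2", provided inclusion criteria 2 and 4 are met. Criterion 2 supplies the time limit: "For Objective 2, patient assessment should occur ideally within 14 days but not more than 30 days from diagnosis". Criterion 4 requires at least 3 months of planned therapy. Section 9.2.4 also says that an early outcome event is no reason to leave a patient out.

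**How they are analysed.** Protocol 9.7.2.1 describes the propensity score as the probability of being initiated on DE. SAP (Objective 2) 6.1 says: "The start of the follow up will be defined as the initiation of each of these two treatments". SAP 6.7 says that "data up to the start of dabigatran or VKA treatment will be considered as baseline and will be used as model covariates". SAP 7.6 names the groups as "patients initiating VKA at baseline, and patients initiating DE at baseline". The treated and restricted sets in SAP 6.3 require eligibility and at least one intake, and the restricted set adds propensity score overlap. None requires new use.

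**What is adjusted for.** Table 7.6:1 (propensity score) and Table 7.6:2 (Cox model) both include previous VTE and bleeding history. Neither lists anticoagulant use at the index event, an earlier agent, or switching.

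**The concern.** The main analysis is written for patients starting DE or VKA for a new VTE, but eligibility also admits two other kinds of patient.

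- **Ongoing users.** Inclusion 2 requires a new acute VTE, so a patient on continuing treatment for an earlier VTE has had the index event while prescribed an anticoagulant. Such a patient may have a higher recurrence risk. Having already tolerated the drug, the patient may have a lower bleeding risk.
- **Early switchers.** A patient moved to DE or VKA within 30 days may have been moved because of an early event or intolerance. The rules permit this; the documents give no reasons for switching.

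If either kind is unevenly split between the arms, the hazard ratio for both primary outcomes mixes the drug effect with the difference in patient type. Overlap weighting balances what is in the propensity model, and these features are not in it. Separately, the start of follow-up is not defined for someone already taking the drug at diagnosis.

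**Working it through.** **1. Do the variable lists stand in for the missing features?** Only in part.
- Previous VTE (both tables) is true for every ongoing user, but also for patients whose earlier treatment had ended. Weighting equalises the share with previous VTE; it does not equalise, within that group, the share on treatment at the index event.
- Major and gastrointestinal bleeding history at any time is in both tables, and SAP 6.7 takes data up to drug start. A switcher whose earlier bleed was major or gastrointestinal is therefore partly covered. Other bleeds and other reasons for switching are not.

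**2. Time zero, side by side.**
- Protocol 9.3.2: primary, secondary and further outcomes run from index diagnosis to 12 months after it.
- SAP 5.2: secondary outcomes run from index diagnosis.
- SAP 6.1: follow-up starts at initiation of DE or VKA.
- SAP 7.8: exposure is the days from first to last intake, inclusive, with no truncation at diagnosis.
- SAP 4: no change to the planned analysis.

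The two starting points differ. For a switcher, an event between diagnosis and the switch is an outcome under Protocol 9.3.2, but it precedes follow-up under SAP 6.1. If it was a major bleed, it can become a covariate under SAP 6.7. For an ongoing user, the text does not say which date counts as initiation.

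**3. The plan's own figure.** Protocol Table 9.5:2 uses VKA 7.7%, DE 5.3%, HR 0.69, one-sided alpha 0.025, 90% power, 15% loss and the Freedman formula, giving N = 5000.
- Events required = (1.960 + 1.282)² × ((1 + HR)/(1 − HR))². At HR 0.69 this is 10.51 × 29.7 ≈ 312.
- With loss spread exponentially over the year, the mean event probability is about 0.0604, so N ≈ 5170. At HR 0.685, which rounds to 0.69, N = 5000. The table reproduces and is not in dispute.
- At N = 5000 and HR 0.69, about 302 events are expected. Power = Φ(√302 × 0.31/1.69 − 1.96) = 0.890.

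**4. Size of the bias (illustration).** Assume constant hazards and no adjustment. Let a share p of the VKA arm and q of the DE arm be ongoing users, with hazard r times that of new users.

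Apparent HR = true HR × (1 − q + q·r) / (1 − p + p·r)

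With q = 0:

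| p | r | Divisor | True HR 1.0 | True HR 0.69 |
|---|---|---|---|---|
| 10% | 0.5 | 0.95 | 1.05 | 0.73 |
| 20% | 0.5 | 0.90 | 1.11 | 0.77 |
| 10% | 2 | 1.10 | 0.91 | 0.63 |
| 20% | 2 | 1.20 | 0.83 | 0.58 |

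If instead q = 10% and p = 0, a true HR of 1.0 becomes 0.95 at r = 0.5 and 1.10 at r = 2. The direction depends on which arm holds these patients and on whether their hazard is lower or higher. The values of p, q and r are assumptions; none is in the documents.

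**5. Precision cost of a new-user set.** If restriction removes a share f of the 5000 patients, events fall to 302 × (1 − f). Power at HR 0.69 is then 0.874 (f = 5%), 0.856 (10%), 0.814 (20%) or 0.760 (30%). The documents give no value for f, and these figures ignore weighting and as-treated censoring.

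**The case against.** Non-restrictive entry is deliberate (Protocol 9.9), so making a new-user set the main analysis is a matter of judgement. Previous VTE and bleeding history give partial adjustment, and the 30-day limit with 3 months of planned therapy narrows the switcher group. SAP 5.3, 6.4 and 7.7 and Protocol 9.7.2.2 are not in the public text and could hold a relevant subgroup. All of this stands. A subgroup would not, however, change the propensity score list or the time zero, both of which are visible.

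Three stronger readings are tempting, and the documents do not support them.

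- **A clock starting years before the index event.** A reader might take SAP 6.1 literally and count long event-free VKA time before the index VTE. Protocol 9.3.2 counts outcomes from index diagnosis, SAP 6.1 ties the groups to what is prescribed at baseline and at discharge or 14 days, and SAP 7.6 speaks of initiation at baseline. Together they make treatment for the index event the likelier meaning. What stands is that the start is undefined for ongoing users. No size should be built on the literal reading.
- **A one-sided bias against or for VKA.** A reader might infer from the recent NOAC approval (Protocol 7.3) that ongoing users all fall in the VKA arm. Grouping follows the drug prescribed for the new event, so a patient whose VTE occurred on VKA and who is moved to DE enters the DE arm. Switchers can enter either arm.
- **Switchers without a group.** A reader might infer that a patient switched after the discharge or 14-day reading cannot be assigned. SAP 6.1 also uses the Patient Status eCRF obtained at enrolment, which may settle it.

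**Conclusion.** The concern holds in a limited form. Ongoing users and early switchers are admitted, the analysis describes everyone as an initiator, and the visible models have no direct term for either feature. The DE versus VKA hazard ratio for both primary outcomes can be biased in either direction. The size cannot be stated, because it depends on how many such patients each arm holds and on their relative hazard. Under the assumptions shown, with 10% to 20% of one arm affected and hazards between half and double, the apparent ratio moves by roughly 5% to 20%, before any partial adjustment through previous VTE. The mismatch between Protocol 9.3.2 and SAP 6.1 needs no assumption and should be reconciled in any case. That the two features are missing is shown for the visible text only.

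**What to change.** 1. State one time zero, no earlier than index diagnosis, for time at risk, exposure (SAP 7.8) and covariate assessment (SAP 6.7). Define it explicitly for ongoing users, and reconcile Protocol 9.3.2 with SAP 6.1.
2. Add two indicators to Tables 7.6:1 and 7.6:2: on anticoagulation at index diagnosis, and switched from another oral anticoagulant since diagnosis.
3. Report the number of each kind of patient by arm.
4. Add an overlap-weighted Cox analysis restricted to patients not on an oral anticoagulant at index diagnosis whose first oral anticoagulant for the event is DE or VKA. Prespecify it at least as a sensitivity analysis. Whether it should be the main analysis is open.

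The cost is SAP wording, two derived flags and one further analysis, with the loss of precision shown above in the restricted set. No new data collection appears necessary: Protocol 9.3.1.1 lists the diagnosis date, start and stop dates of treatment for the VTE, and current therapies with their indication. That section does not list dates for concomitant therapies, so the ongoing-use flag may be incomplete for some patients. The number who cannot be classified should be reported.
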